3.4 Primary Effectiveness Endpoint

The primary effectiveness endpoint is acute success defined as rate of successful pulmonary vein electrical isolation with confirmation of entrance/exit block.

The rate of acute success will be presented as a binomial rate (N events/ N subjects) with corresponding exact binomial 95% confidence interval. The rates will be compared to the acute success rates derived from available literature data.

The primary effectiveness endpoint will be assessed in all enrolled subjects who undertake the ablation procedure to the point that the Cryoablation Balloon is used to deliver at least one cryo application (Treated subjects).

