2 SUBJECT CLASSIFICATION DEFINITIONS

For the purposes of this clinical study, the following definitions regarding the status of a subject will apply:

Enrolled Subject - Any subject who has signed an informed consent form (ICF)

Consent Ineligible Subject – Any subject who has signed the informed consent but is found not to meet all the inclusion/exclusion criteria. This includes a subject who has signed an informed consent form but may be excluded based on the results of the pre-procedure TEE or intracardiac echocardiogram (ICE) evaluation of the left atrial appendage (LAA) and/or PV anatomy. In the event these subjects completed a trans-septal puncture, they will be followed through discharge for the recording of any procedure related adverse events. These subjects will not count towards the enrollment ceiling and will not be considered for the primary endpoints analysis.

Intent Subject – Any subject who has signed an informed consent form (ICF) and is deemed study eligible by meeting all the inclusion and none of the exclusion criteria but does not undergo the ablation procedure. This subject will be withdrawn from the study. Data will be collected up to the point of withdrawal, will not count towards the enrollment ceiling and will not be considered for primary endpoints analysis.

Attempt Subject - Any subject who has signed an informed consent form (ICF) and is deemed study eligible by meeting all the inclusion and none of the exclusion/criteria and undergoes the ablation procedure with any of the investigational device entered in the subjects' body but no energy is delivered to the PVs. This subject will be followed through the 30 days follow up then withdrawn from the study. Data will be collected up to the point of withdrawal, will not count towards the enrollment ceiling and will not be considered for primary endpoints analysis.

Treated Subject – Any screened subject who completes the ablation procedure to the point that any of the investigational products are introduced into the body and Cryo-energy is delivered. Enrolled subjects will be followed for all study outcome measures for the full duration of the clinical study.

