3 ENDPOINT ANALYSES

3.1 Analysis Details

3.1.1 Analysis Populations

The overall analysis of the endpoints of the study will be based on the Enrolled Subject Population. All Enrolled subjects will be included in this analysis and the analysis will be

performed when all subjects have exited the study (either reaching End of Study or having been withdrawn) and all data cleaning activities have occurred.

A sub-analysis will be performed on the first 30 enrolled subjects when they have reached 1 Month of follow up for the purpose of CE Mark. This analysis will include all data on the first 30 subjects enrolled, as determined based on their enrollment date, and will occur when all data cleaning activities on the submission data have occurred.

An additional sub-analysis will be performed on the first 50 enrolled subjects, determined by enrollment date, for the purpose of PMDA submission. The analysis will occur when the first 50 enrolled subjects have reached a minimum of 1 month of follow up and all data cleaning activities on the submission data have occurred. Submission data will include all available data on the 50 subject cohort, including up to 12 months of follow up. Enrollment date will be considered the date informed consent was signed. When determining the 50 subject cutoff, in the event more than one subject are consented on the same day if subjects are consented at the same site, the first consented subject based on subject ID number will be included. If subjects are consented at different sites both will be included.

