3.1.3 Control of Bias

Selection of subjects for the overall study will be made from the Investigator's standard of care population. All subjects meeting the eligibility criteria and having signed the ICF will be eligible for enrollment in the study and all enrolled subjects will be included in the overall analysis.

Sample sizes for the sub-analyses were determined in conjunction with the corresponding regulatory body prior to performing the data analysis. Subject eligibility for each analysis was determined based on the order of subject enrollment.

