3.2 Statistical Analysis

Analysis of study endpoints will be performed on an intent-to-treat basis. All partial data that is available on subjects who drop out during the course of the study will be included.

Descriptive analysis will be used to present the study. Continuous variables will be reported as median and range, mean \pm standard deviation; categorical variables will be reported as n/N (%).

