3.5 Additional Effectiveness Endpoint

The additional effectiveness endpoint is 12 month treatment success, defined as the proportion of subjects free from symptomatic atrial arrhythmias at 12 months.

The rate of 12 month success will be presented as a binomial rate (N events/ N subjects) with corresponding exact binomial 95% confidence interval. The rates will be compared to the 12 month success rates derived from available literature data.

The additional effectiveness endpoint will be assessed in all enrolled subjects who undertake the ablation procedure to the point that the Cryoablation Balloon is used to deliver at least one cryo application (Treated subjects). Subjects who withdraw from the study prior to their 12 month visit without experiencing an event will be considered ineligible for this analysis.

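### The SAP promises an all-enrolled, intent-to-treat analysis, but both effectiveness endpoints are confined to Treated subjects, so any eligible subject in whom the device was tried without cryo delivery leaves the denominator

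*SAP*

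**What the plan says.** Three general statements describe a broad population. Section 3.1.1: "The overall analysis of the endpoints of the study will be based on the Enrolled Subject Population". Section 3.1.3, under control of bias: "all enrolled subjects will be included in the overall analysis". Section 3.2: "Analysis of study endpoints will be performed on an intent-to-treat basis". Section 2 defines an enrolled subject as anyone who has signed consent.

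The endpoint sections use a narrower set. Section 3.4 assesses acute success only in subjects who go "to the point that the Cryoablation Balloon is used to deliver at least one cryo application (Treated subjects"). Section 3.5 uses the same set for 12-month success.

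Section 2 defines the group that falls between the two. An Attempt subject has consented, meets every eligibility criterion and "undergoes the ablation procedure with any of the investigational device entered in the subjects' body but no energy is delivered to the PVs". Such subjects are followed to 30 days and then withdrawn, and their data "will not count towards the enrollment ceiling and will not be considered for primary endpoints analysis".

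Section 3.3 nevertheless assesses the primary safety endpoint in Attempt and Treated subjects together.

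**The concern.** The general statements and the endpoint-specific ones cannot all hold, because a set restricted to subjects who received cryo is neither all enrolled nor intent-to-treat. The subjects removed are also not neutral for effectiveness: they are eligible, the device was tried, and no vein was treated. A supporting rate that includes them is not planned anywhere in the SAP.

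Acute success is the primary effectiveness endpoint. Both effectiveness rates are to be set against literature rates, and early cohorts of 30 and 50 subjects feed regulatory submissions. A reader who relies on the intent-to-treat label would take the reported rate to cover everyone in whom treatment was intended or tried, which it does not.

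**Working it through.** **Status of an Attempt subject on each endpoint**

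- Acute success (1.4.2) needs demonstrated isolation of at least 3 veins at the end of the first procedure. With no energy delivered to any vein, the subject cannot be an acute success.
- 12-month success (1.4.3) counts an acute procedural failure as a treatment failure. The subject can therefore be classified without 12-month data, although follow-up stops at 30 days.

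**Effect on the rate**

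Let s be the successes among N Treated subjects and k the number of Attempt subjects.

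- Treated-only rate: s/N
- Attempt-plus-Treated rate, Attempt subjects as failures: s/(N + k)
- Difference: s/N − s/(N + k) = s·k / [N(N + k)]

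The difference is zero when k = 0 and positive whenever k ≥ 1 and s > 0. It has one direction.

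**Inputs**

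The SAP states no expected success rate and no Attempt count, and its sample size section is redacted, so there is no planned figure to reproduce. The values of s and k below are assumptions. Intervals are exact binomial 95% intervals, as sections 3.4 and 3.5 specify.

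*Full study.* Section 1.1 gives 100 subjects. Attempt subjects do not count towards the enrollment ceiling, so they are added on top of N = 100. Assume s = 98.

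| Attempt subjects k | s/(N + k) | Rate | 95% CI |
|---|---|---|---|
| 0 | 98/100 | 98.0% | 93.0–99.8 |
| 1 | 98/101 | 97.0% | 91.6–99.4 |
| 3 | 98/103 | 95.1% | 89.0–98.4 |
| 5 | 98/105 | 93.3% | 86.7–97.3 |

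Check for k = 3: 98 × 3 / (100 × 103) = 294/10,300 = 2.85 percentage points.

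*First 30 enrolled.* Section 3.1.1 fixes this cohort by enrollment date, and enrollment means signed consent. Attempt subjects therefore sit inside the 30 and are not added to it. Assume 2 Attempt subjects, 28 Treated and 27 acute successes.

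- Treated only: 27/28 = 96.4% (81.7–99.9)
- Attempt plus Treated: 27/30 = 90.0% (73.5–97.9)
- Difference: 27 × 2 / (28 × 30) = 54/840 = 6.4 percentage points

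*12-month success.* Assume 70 successes in 100 Treated subjects and no event-free withdrawals: 70/100 = 70.0% becomes 70/103 = 68.0% with 3 Attempt subjects.

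**The case against.** The strongest reply is that the restriction is pre-specified and open. Section 2 says that Attempt subjects are left out of the primary endpoints, and sections 3.4 and 3.5 name the Treated set where the endpoints are analysed. Both endpoint sections can be read as narrowing the general statement, since they start from enrolled subjects and then add a condition. A Treated-only rate also answers a coherent question, namely how often isolation is achieved once the device is used. The analysis is descriptive, and if the literature rates are treated-only too, that denominator is the like-for-like one.

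Much of this stands. A reader might infer that the plan conceals the exclusion; it does not. The Treated-only rate should stay. But the SAP never says that the endpoint sections override 3.1.1, 3.1.3 and 3.2, and a correct rule elsewhere does not make the intent-to-treat label true. The literature denominators are not given, so the like-for-like argument cannot be checked; reporting both rates covers either case.

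Two other stronger readings also fail:

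- A reader might infer that device failures as a class drop out. An Attempt subject may have been stopped for access, anatomy or another reason unrelated to the device, and a failure after the first cryo application stays in the denominator.
- A reader might infer that a literal all-enrolled analysis is needed. That would bring in consent-ineligible subjects and eligible subjects who never had the procedure, who say little about the device. Section 3.3 already points to the more natural set.

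**Conclusion.** The inconsistency is plain in the text: the SAP claims a property for its effectiveness analyses that they do not have, and it plans no supporting rate to show what the restriction does.

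It would go too far to say that acute success is overstated in this trial. The SAP gives no Attempt count, and with none the rates are identical. What can be said is conditional: if Attempt subjects occur, both Treated-only rates lie above the rates among all subjects in whom the device was tried. Under the assumed counts, the gap is about 1 percentage point per Attempt subject at 100 Treated and about 3 points each in the 30-subject cohort. This rests on counting Attempt subjects as failures, which follows from 1.4.2 and 1.4.3. The point concerns effectiveness only.

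**What to change.** 1. **Sections 3.4 and 3.5.** Keep the Treated-only rate. Beside it, report an Attempt-plus-Treated rate with the same exact interval, counting Attempt subjects as acute and 12-month failures.
2. **Section 3.5.** State that Attempt subjects, although withdrawn after 30 days, do not come under the rule "Subjects who withdraw from the study prior to their 12 month visit without experiencing an event will be considered ineligible for this analysis". Otherwise that rule could remove them again. Its effect on other withdrawals is a separate matter.
3. **Section 2.** Amend the sentence that bars Attempt subjects from the primary endpoints so that it permits the new rate. As it stands it also conflicts with section 3.3.
4. **Sections 3.1.1, 3.1.3 and 3.2.** For effectiveness, replace the Enrolled, all-enrolled and intent-to-treat wording with the populations actually used.
5. **Entry criterion.** Section 2 admits an Attempt subject on entry of any study device, whereas section 3.3 asks for insertion of the balloon. State which one defines the combined set.

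The cost is a wording amendment and one more binomial rate per endpoint, from data already collected. The downside is a slightly lower supporting success rate if Attempt subjects occur.

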3.5 Additional Effectiveness Endpoint

The additional effectiveness endpoint is 12 month treatment success, defined as the proportion of subjects free from symptomatic atrial arrhythmias at 12 months.

The rate of 12 month success will be presented as a binomial rate (N events/ N subjects) with corresponding exact binomial 95% confidence interval. The rates will be compared to the 12 month success rates derived from available literature data.

The additional effectiveness endpoint will be assessed in all enrolled subjects who undertake the ablation procedure to the point that the Cryoablation Balloon is used to deliver at least one cryo application (Treated subjects). Subjects who withdraw from the study prior to their 12 month visit without experiencing an event will be considered ineligible for this analysis.

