1.4.3 Additional Effectiveness Endpoint: 12 Month Treatment Success

Treatment success is defined as the proportion of subjects free from symptomatic atrial arrhythmias at 12 months. A treatment failure is defined as a subject being an acute procedural failure, having more than one repeat procedure during the 90-day blanking period or having a documented, symptomatic episode(s) of atrial fibrillation or atrial tachycardia, between 91 and 365 days post index procedure (windows allowed per protocol as shown in Table 2 included). Occurrence or recurrence of a right atrial arrhythmia is not considered a treatment failure post the 90-day blanking period.

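### The 12-month success rate drops early withdrawals only if they had no event, so its denominator depends on the outcome, and the SAP plans no other estimate beside it

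*SAP*

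**What the plan says.** Section 3.5 assesses 12-month treatment success in Treated subjects and names one estimator: "The rate of 12 month success will be presented as a binomial rate (N events/ N subjects"), with an exact 95% confidence interval, to be compared with rates from the literature. It then adds: "Subjects who withdraw from the study prior to their 12 month visit without experiencing an event will be considered ineligible for this analysis".

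Section 1.4.3 defines failure in three ways: acute procedural failure, "having more than one repeat procedure during the 90-day blanking period", or a documented symptomatic atrial arrhythmia "between 91 and 365 days post index procedure (windows allowed per protocol as shown in Table 2 included").

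The general rules read differently. Section 3.2 states: "Analysis of study endpoints will be performed on an intent-to-treat basis", and: "All partial data that is available on subjects who drop out during the course of the study will be included". Section 3.1.3 lists as a control of bias that "all enrolled subjects will be included in the overall analysis".

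The SAP contains no censored estimate, imputation or bound for this endpoint.

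**The concern.** Take two subjects who withdraw on the same day in month 8. The one who has already had a recurrence is kept and counted as a failure; the one who has not is removed. Whether a withdrawn subject enters the denominator is therefore decided by the outcome being measured. Failures among withdrawals are retained while the successes they would have been set against are not.

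Sections 3.2 and 3.1.3 tell the reader that dropouts' data and all enrolled subjects are included. Section 3.5 can be read as a specific exception, but no section says so.

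The word 'event' adds an ambiguity. In the rate formula of section 3.5 it means a success; in the exclusion sentence it must mean a failure. If a programmer read it there as arrhythmia only, an acute procedural failure who then withdrew would be dropped, which raises the success rate.

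At stake is the comparison with published 12-month rates: the reader would see one proportion with no planned statement of how far attrition could have moved it.

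**Working it through.** **Inputs.** The SAP shows no success or withdrawal rate to reproduce (the sample size section, 3.1.2, is redacted), so the rates below are assumptions. From the SAP: about 100 subjects (section 1.1), arrhythmia failures counted on days 91-365 (section 1.4.3), and the exclusion rule (section 3.5). Assumed: true success S = 70%, failures uniform over days 91-365, acute failures ignored, and 5%, 10% or 20% withdrawing.

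**1. Withdrawal unrelated to outcome.** Let d be the share who withdraw and pf the probability of failing before withdrawal. Completers contribute (1-d), of whom S succeed; withdrawals contribute only their failures, d·pf. So

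expected planned rate = (1-d)S / [(1-d) + d·pf].

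- All leave by day 90: pf = 0.
- Uniform over the year: pf = 0.30 × (275/365) × 0.5 = 0.113.
- All leave after day 90, uniformly: pf = 0.30 × 0.5 = 0.15.

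| Withdrawal time | d = 5% | d = 10% | d = 20% |
|---|---|---|---|
| by day 90 | 70.0% | 70.0% | 70.0% |
| uniform over the year | 69.6% | 69.1% | 68.1% |
| after day 90 | 69.5% | 68.9% | 67.5% |

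The largest bias for S between 60% and 80% is at S = 60%, d = 20%, all after day 90: 0.8 × 0.6 / (0.8 + 0.2 × 0.2) = 57.1%, or -2.9 points. At S = 80% the same case gives 78.0%, or -2.0 points.

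A simulation (4,000 runs, 100 subjects, withdrawal uniform over the year) gave planned rates of 69.1% and 68.1% at d = 10% and 20%, with SDs of 4.9 and 5.1 points. Kaplan-Meier gave 70.0% in both cases.

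**2. Withdrawal related to outcome.** Let w be event-free withdrawals as a share of Treated subjects and f the share of them who would have failed.

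- Planned rate = [S - w(1-f)] / (1-w); bias = w[f - (1-S)] / (1-w). It is positive when f exceeds the overall failure share, and at most w·f.
- Kaplan-Meier, with observed failures F = (1-S) - w·f and withdrawals both uniform over days 91-365: (1-F-w)^(F/(F+w)).
- Bounds: S - w(1-f) with all such withdrawals counted as failures; add w for all counted as successes.

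| f | Estimate | w = 5% | w = 10% | w = 20% |
|---|---|---|---|---|
| 0 | planned | 68.4% | 66.7% | 62.5% |
| 0 | Kaplan-Meier | 69.1% | 68.2% | 66.0% |
| 0.5 | planned | 71.1% | 72.2% | 75.0% |
| 0.5 | Kaplan-Meier | 71.7% | 73.5% | 77.5% |
| 1 | planned | 73.7% | 77.8% | 87.5% |
| 1 | Kaplan-Meier | 74.3% | 78.8% | 88.8% |

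When future failures leave, Kaplan-Meier is slightly further from 70% than the planned rule. Only the bounds always contain 70%; at w = 10%, f = 0.5 they are 65% and 75%.

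**3. Worked counts, 100 Treated subjects (exact 95% CIs).**

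| Event-free withdrawals | Planned | All counted as failures | All counted as successes |
|---|---|---|---|
| 10 | 63/90 = 70.0% (59.4-79.2) | 63.0% (52.8-72.4) | 73.0% (63.2-81.4) |
| 20 | 56/80 = 70.0% (58.7-79.7) | 56.0% (45.7-65.9) | 76.0% (66.4-84.0) |

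The same 70% stands for bounds 10 points wide in one case and 20 in the other.

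**The case against.** The rule is a known-outcome rule fixed in advance. Failure is absorbing, so a subject who fails and then leaves has a known 12-month outcome, and one who leaves event-free does not. Dropping both would discard observed failures. Counting failures seen before withdrawal does use partial data, and a specific rule normally overrides a general one. Section 3.1.3 is mainly about selection, and section 3.5 already restricts the endpoint to Treated subjects. The bias under random withdrawal is small and runs against the device; the large upward figures need leavers to fail far more often than others, which nothing in the SAP suggests. Kaplan-Meier does not cure informative withdrawal. In the full cohort a reader could derive the number excluded and both bounds, because "categorical variables will be reported as n/N" and the Treated count would be known. The protocol, which is not shown, may plan more.

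Most of this stands and limits the weight of the point. It is why the planned proportion should be kept and why the bounds matter more than the Kaplan-Meier estimate. The mismatch with section 3.1.3 is weak support. It does not remove the core: followed exactly, the rule gives a biased rate even when withdrawal after day 90 is random, the SAP plans neither a censored estimate nor intervals for the bounds, and sections 3.2 and 3.5 are not reconciled.

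**Conclusion.** The concern holds, as a minor one. The denominator depends on the outcome, and this SAP names no other estimate for the endpoint. Under non-informative withdrawal the success rate is understated by 0 to 2.9 points (assumed success 60-80%, withdrawal up to 20%, failures uniform over days 91-365), which is below the sampling error at 100 subjects. Under informative withdrawal the direction is open, and the SAP's single estimate would not reveal it. The endpoint is additional and descriptive, with no visible test or performance goal; the practical consequence is confined to the comparison with literature rates.

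**What to change.** Keep the section 3.5 proportion with its exact interval, and state that 'event' in the exclusion sentence means any treatment failure under section 1.4.3, including acute procedural failure. Report beside it, in all Treated subjects:

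- **The number excluded and both bounds**: the proportions with every event-free withdrawal counted as a failure and as a success, each with an exact 95% CI.
- **A Kaplan-Meier estimate at day 365** with a log-log 95% CI. Suggested wording: *Acute procedural failure is an event at day 0. A second repeat procedure within the blanking period is an event on its date. Other failures up to the 12-month visit, within its protocol window, are events on the actual day or day 365, whichever is earlier. Subjects event-free at that visit are censored at day 365, after any failure on that day. Event-free withdrawals are censored at their last rhythm assessment.* State that this removes the bias only if withdrawal is non-informative.

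In section 3.2 add *except as stated in section 3.5*. If the 12-month rate is reported for the PMDA cohort, say that subjects still in follow-up are censored.

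The cost is SAP wording, one Kaplan-Meier estimate, two proportions and one count, with no new data. The downside is a few extra outputs on a descriptive endpoint and an asymptotic Kaplan-Meier interval.

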1 PROTOCOL SUMMARY

1.1 Study design

The study is a non-randomized, open label, prospective multi-center, clinical study designed to collect long-term (1 year), system-related, clinical and subject reported outcome data from subjects indicated for a de novo ablation of paroxysmal atrial fibrillation and treated with the Cryterion Cardiac Cryoablation System and components including the SmartFreeze Cryo-console, the Cryoablation Balloon Catheter, and the Circular Mapping catheter.

A protocol amendment of the original FIM protocol was initiated in May 2018 designed for the purpose of obtaining CE mark and intended to prolong the follow-up period from 30 days to 12 months and extend the number of enrolled subjects from 30 to 100.

Subjects will be followed for 12 months by each clinical center with specific scheduled visits to detect recurrent AF (Detectable AF) and adverse events (AEs).

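### Under SAP 1.4.3 and 3.5 together, a Treated subject who has not withdrawn counts as a 12-month success even if no 12-month assessment was made

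*SAP*

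**What the plan says.** SAP 1.4.3 states the endpoint as follows: "Treatment success is defined as the proportion of subjects free from symptomatic atrial arrhythmias at 12 months". Failure is then listed. The procedural part reads "A treatment failure is defined as a subject being an acute procedural failure, having more than one repeat procedure during the 90-day blanking period". The arrhythmia part reads "having a documented, symptomatic episode(s) of atrial fibrillation or atrial tachycardia, between 91 and 365 days post index procedure", with protocol visit windows allowed. Neither death nor missing rhythm data is in the list.

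SAP 3.5 takes all Treated subjects (at least one cryo application) as the analysis set and reports a binomial rate with an exact 95% confidence interval, to be compared with literature rates. Its only exclusion is: "Subjects who withdraw from the study prior to their 12 month visit without experiencing an event will be considered ineligible for this analysis".

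SAP 3.2 adds that available partial data on drop-outs are included. It gives no rule for a missing rhythm assessment. SAP 3.1.1 describes exit from the study as "either reaching End of Study or having been withdrawn".

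**The concern.** After blanking, failure has to be documented, and SAP 1.1 says that the scheduled visits are there to detect recurrent AF. A subject who does not attend has little opportunity to produce the documentation that failure requires. If that subject has not withdrawn, nothing in 3.5 removes them from the rate, so lack of observation is recorded as treatment success.

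The rate comes from an open-label, single-arm study and is to be set beside literature rates, so the classification of unobserved subjects feeds directly into that comparison. The exact binomial interval reflects sampling error only and takes every classification as known.

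**Working it through.** **Step 1: where each kind of Treated subject falls.**

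| Treated subject | Failure under 1.4.3? | Excluded under 3.5? | Result |
|---|---|---|---|
| Acute failure, more than one repeat in blanking, or documented symptomatic AF/AT on days 91-365 | Yes | No | Failure |
| Event-free, withdraws before the 12-month visit | No | Yes | Out of the rate |
| Event-free, attends the 12-month visit | No | No | Success, properly |
| Event-free, still in the study, no 12-month assessment | No | No | Success by default |
| Event-free, dies or is lost before 12 months | No | Not stated | Out of the rate if this is a withdrawal, otherwise success |

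The fourth row is the defect. The fifth is an ambiguity: 3.1.1 names two ways to exit and assigns death and loss to follow-up to neither. Whichever way it is resolved, death is not in itself a failure.

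**Step 2: size.** The SAP gives no expected rate for this endpoint, and its sample size section is redacted, so there is no planned figure to reproduce. What follows illustrates the effect with the SAP's own estimator, a binomial proportion with Clopper-Pearson 95% limits.

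Inputs:
- N = 100 treated. SAP 1.1 gives 100 as the extended enrolment; that all are treated is assumed.
- f = 20 or 30 documented failures (assumed).
- m = 1 to 15 event-free, non-withdrawn subjects without a 12-month assessment (assumed).

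Formulas:
- as written: (N − f)/N
- unassessed excluded: (N − f − m)/(N − m)
- unassessed as failures: (N − f − m)/N

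| f | m | As written | Excluded | As failures |
|---|---|---|---|---|
| 20 | 1 | 80/100 = 80.0% | 79/99 = 79.8% | 79/100 = 79.0% |
| 20 | 2 | 80.0% | 78/98 = 79.6% | 78/100 = 78.0% |
| 20 | 5 | 80.0% | 75/95 = 78.9% | 75/100 = 75.0% |
| 20 | 10 | 80.0% (70.8-87.3) | 70/90 = 77.8% (67.8-85.9) | 70/100 = 70.0% (60.0-78.8) |
| 20 | 15 | 80.0% | 65/85 = 76.5% | 65/100 = 65.0% |
| 30 | 10 | 70/100 = 70.0% (60.0-78.8) | 60/90 = 66.7% (55.9-76.3) | 60/100 = 60.0% (49.7-69.7) |

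The as-written column does not change with m: the rule gives the same rate and the same interval whether 0 or 15 subjects were unassessed.

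**Step 3: cross-check.** If unassessed subjects have the same true success probability s as the rest, the expected inflation is (m/N) × (1 − s). With m = 10 and s = 0.778 this is 0.10 × 0.222 = 2.2 points, which matches 80.0 − 77.8. For s between 0.80 and 0.70, m = 10 gives +2.0 to +3.0 points. The upper bound is m points per 100 treated, reached if every unassessed subject had in fact failed.

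**The case against.** The strongest reply is that the SAP nowhere states that unobserved subjects are successes. It defines success as freedom from arrhythmia at 12 months, and a subject with no information at 12 months has not been shown to meet that. This is fair as to intent. But 3.5 fixes the denominator and its one exclusion, and 1.4.3 fixes the failure list. A programmer who applies both literally has only the success category left for such a subject.

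A reader might infer more than the text supports:

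- **That every death or loss to follow-up is counted as a success.** SAP 3.1.1 offers only two exits, and SAP section 2 uses withdrawal for exits that the plan itself imposes, so the word is not confined to withdrawn consent. Deaths and losses may well be withdrawals, and then they are excluded. The text leaves this open.
- **That missing any visit makes a success false.** A subject who misses month 3 or month 6 but attends at month 12 without a failure event is reasonably evaluable.
- **That early subjects who finished under 30-day follow-up are scored as successes.** The amendment was "intended to prolong the follow-up period from 30 days to 12 months", but the SAP does not show that anyone left at 30 days or how such an exit was recorded. It says that subjects are followed for 12 months.

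Three further points stand. The size rests wholly on assumed counts, and a 2 to 3 point shift is small beside an interval of 87.3 − 70.8 = 16.5 points. One or two subjects move the rate by at most 0.4 points against exclusion, or 2 points against counting them as failures. Deaths are not hidden either: device- or procedure-related death is a listed safety event in 1.4.1, and 3.3 provides listings. That does not correct the effectiveness rate, but it limits the harm.

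**Conclusion.** The point holds for one group: Treated subjects who remain in the study, have no documented failure and have no 12-month assessment. For them 1.4.3 and 3.5 together produce a success that nobody observed. The SAP sets this eligibility rule itself and leaves only the visit windows to the protocol. For death and loss to follow-up the finding is that the rule is ambiguous; it cannot be said that these subjects are counted as arrhythmia-free.

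This part of the rule can only push the rate up. The amount is unknown. With 100 treated, 20 documented failures and 10 unassessed (all assumed), the rate as written is 2.2 points above exclusion and 10 points above counting them as failures. The endpoint is an additional one in a descriptive analysis, so the change should be made, but the primary endpoints do not depend on it.

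**What to change.** In SAP 3.5:

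1. Count a subject as a success in the binomial rate only if there is no failure event and the 12-month assessment was completed within the protocol window. Treat every other event-free Treated subject as not evaluable, whatever the reason (withdrawal, loss to follow-up, death, missed 12-month visit), and show the counts by reason beside the rate.
2. Add a Kaplan-Meier estimate at 12 months that censors event-free subjects at their last rhythm assessment. Step 1 alone keeps every early failure but drops subjects who were observed event-free for part of the year, so it can bias the rate downward. The Kaplan-Meier estimate uses that partial follow-up, in line with the statement on partial data in 3.2.
3. Add one worst-case sensitivity rate in which all not-evaluable subjects, deaths included, count as failures. Keeping death as a failure in this row only leaves the endpoint definition in 1.4.3 unchanged.

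The cost is some SAP wording, two extra table rows, a slightly smaller evaluable denominator and a possibly lower reported rate.
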